### SLF (Grade 3 or Higher) and Unacceptable Lens Fitting

- With Borrowing

```
PROC MCMC DATA= ADS DIC =brief
NBI=50000 NMC=80000 THIN=15 STATS=ALL MONITOR=( parms_ ) STATS(ALPHA=(0.05)
PERCENTAGE=(2.5 25 50 75 97.5) ) SEED=14789652 ;
PARM p ro .5 ;
PRIOR ro ~ UNIFORM(0,1);
PRIOR p ~ BETA(0.5, 0.5);
BEGINCNST;
IF studyid in [REDACTED] ) THEN a0 = 0.3;
ELSE IF studyid in ( [REDACTED] THEN a0 = 0.3;
ELSE IF studyid in [REDACTED] ) THEN a0=0.1;
ENDCNST;
llike = log( (1-ro)*PDF('BINOMIAL', y, p, 2) + z*ro*(p**y*(1-p)**(2-y))***(1/2) );
IF studyid in ( [REDACTED] ) THEN llike = llike; ELSE llike = a0*llike;
MODEL y ~ GENERAL(llike);
RUN;
```

- Without Borrowing

```
PROC MCMC DATA= ADS DIC =brief
NBI=50000 NMC=80000 THIN=15 STATS=ALL MONITOR=( parms_ ) STATS(ALPHA=(0.05)
PERCENTAGE=(2.5 25 50 75 97.5) ) SEED=14256983 ;
PARM p ro .5 ;
PRIOR ro ~ UNIFORM(0,1);
PRIOR p ~ BETA(0.5, 0.5);
BEGINCNST;
IF studyid in [REDACTED] ) THEN a0 = 0;
ELSE IF studyid in ( [REDACTED] ) THEN a0 = 0;
ELSE IF studyid in [REDACTED] ) THEN a0=0;
ENDCNST;
llike = log( (1-ro)*PDF('BINOMIAL', y, p, 2) + z*ro*(p**y*(1-p)**(2-y))***(1/2) );
IF studyid in ( [REDACTED] ) THEN llike = llike; ELSE llike = a0*llike;
MODEL y ~ GENERAL(llike);
RUN;
```

Where,

ads = Analysis dataset for Grade 3 or higher SLFs or Unacceptable Lens Fitting

a0 = degree of borrowing

studyid=Study Identifier

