**CR-6400, Statistical Analysis Plan Version 1.0**

completed. The investigational product in all these studies was the multifocal Test lens in its' final design (FAL100, FAL101 and FAL102) made from different manufacturing platforms.

Table 4: Historical Studies Utilized for Sample Size Calculation

Study	Study Design	Manufacturing Platform	#Enrolled	#Completed	Population	SKU
█	Crossover	FMP 	46	43	Hyperopes	+1.00 to +4.00
█	Crossover	TAM21 	71	61	Hyperopes	+1.00 to +4.00
█	Crossover	TAM21	63	60	Myopes	-1.00 to -4.00
█	Crossover	SCLM 	45	45	Hyperopes	+1.00 to +4.00
█	Parallel	MCLM 	189	168	Myopes	-1.00 to -4.00
█	Crossover	SCLM	40	34	Hyperopes	+1.00 to +4.00
Total			454	411		

FMP: Flexible Manufacturing Platform

TAM21: Tokyo Automatic Machinery -3GT (3rd Generation Technology) manufacturing line

SCLM: Single Cavity Lens Machine

MCLM: Multi Cavity Lens Machine

Summaries of efficacy data pooled across all the 6 studies are presented in Table 5. Results showed that near, intermediate and distance VA have similar variation across studies, therefore a 0.11 was utilized for the variation in the power calculation for all positions. Historical data have shown that the average CLUE vision score of hyperopes is lower that of myopes.

Table 5: Descriptive summary of Efficacy Endpoints Period 1 Only - 2-Week Follow-up

Endpoint	Mean	Median	Standard Deviation	Minimum	Maximum
Distance VA (3m)	-0.077	-0.100	0.1026	-0.320	0.560
Intermediate VA (64cm)	-0.054	-0.060	0.1014	-0.300	0.360
Near VAR (40cm)	0.077	0.060	0.1100	-0.260	0.460
Hyperopes' CLUE Vision score	47.71	48.07	17.514	10.22	93.50
Myopes' CLUE Vision score	56.46	53.37	19.227	21.51	108.04

The proportion of eyes with Grade 3 or higher SLFs and the proportion of eyes with unacceptable lens fittings pooled across all historical studies is presented in the table below. As shown, there was only 1 unacceptable lens fitting in any of the 6 historical study while there have been 5 eyes with reported Grade 3 or higher SLFs.

Table 6: Descriptive Summary of Safety Endpoints all available Data

Endpoint	Test n(%)
Unacceptable lens fitting	1 (0.2)
SLF Grade 3+	5 (1.4)
Total Eyes (N)	350
Total Subjects	175

%= nx100/N

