## Hypothesis Testing

With respect to unacceptable lens fit the null and alternative hypothesis for superiority is as follows:

$$\begin{aligned} H_o &: p_T \geq 0.05 \\ H_A &: p_T < 0.05 \end{aligned}$$

Where,  $p_T$  represents the proportion of subject eyes that are considered to have unacceptable fit for the study lens after 2-weeks of lens wear. Success for unacceptable fit will be declared if the upper bound of the 2-sided 95% credible interval of the proportion is lower than 0.05; i.e.  $P(p_T < 0.05) \geq .975$ .

With respect to Grade 3 or Higher SLFs the null and alternative hypothesis for superiority is as follows:

$$H_o : p_T \geq 0.05$$

$$H_A : p_T < 0.05$$

Where,  $p_T$  represents the proportion of subject that experienced any Grade 3 or Higher SLF or experienced a corneal infiltrate. Success for Grade 3 or higher SLFs will be declared if the upper bound of the 2-sided 95% credible interval of the proportion is lower than 0.05; i.e.  $P(p_T < 0.05) \geq .975$ .

If no SLF findings of Grade 3 or higher or unacceptable lens fit is observed, alternative analysis methods may be considered.

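### With 5,333 retained MCMC draws, simulation error can decide a safety co-primary at some boundary event counts; exact integration of the two-parameter posterior would remove it

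*SAP*

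**What the plan says.** SAP 14.2.1, under the code for Grade 3 or higher slit lamp findings (SLF) and unacceptable lens fitting, runs PROC MCMC with "NBI=50000 NMC=80000 THIN=15 STATS=ALL" and "SEED=14789652". The priors are Beta(0.5, 0.5) for p and uniform on (0,1) for the inter-eye correlation. Historical data enter with a0 = 0.3 or 0.1. The no-borrowing program has the same run length and a different seed.

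SAP 11.1 (Hypothesis Testing) states: "Success for unacceptable fit will be declared if the upper bound of the 2-sided 95% credible interval of the proportion is lower than 0.05", which it equates to a posterior probability of at least .975. The SLF rule is the same: "Success for Grade 3 or higher SLFs will be declared if the upper bound of the 2-sided 95% credible interval" lies below 0.05. SAP 5.1 requires all seven co-primary hypotheses to be met.

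On the historical events, SAP 8.4 reports that "there was only 1 unacceptable lens fitting in any of the 6 historical study while there have been 5 eyes with reported Grade 3 or" worse findings, among 350 eyes. It does not say on which platform these eyes occurred, or whether any belonged to the same subject. Neither document sets a Monte Carlo error limit, a minimum effective sample size, or a rule for a result close to .975.

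**The concern.** Each verdict compares one simulated tail probability with a fixed line. With about 60 subjects and rare events, that probability takes only a few well-separated values, one for each event count. If the value at a plausible count lies closer to .975 than the simulation can resolve, two honest runs of the same program on the same data can disagree. Since all seven co-primaries must pass, such a disagreement would decide whether the lens is declared validated.

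**Working it through.** **Inputs.** Run length, seeds and priors: SAP 14.2.1. Rule: SAP 11.1. From SAP 8.4: historical subjects FMP 23 and TAM21 66 (a0=0.3), pilot line 86 (a0=0.1); historical events 5 SLF eyes and 1 misfit eye; planning rates p=.014, rho=.70 (SLF) and p=.01, rho=.80 (fit). Effective historical subjects: 0.3×89 + 0.1×86 = 35.3.

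**Simulation error.** Retained draws: 80,000/15 = 5,333. For independent draws, SE = sqrt(.975×.025/5,333) = 0.0021. Replicate random-walk Metropolis chains at the printed run length and thinning (two sets, 500 and 300 chains per case) gave 0.0022-0.0025 near .975.

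**Exact posterior.** The SAP 11.1 mixture gives, per subject:
- no eye: (1−rho)(1−p)² + rho(1−p)
- one eye: (1−rho)·2p(1−p)
- both eyes: (1−rho)p² + rho·p

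The posterior is the prior times these terms, raised to the current counts plus the a0-weighted historical counts. Here z in the code is read as 1 when y is 0 or 2. Example: fit, N=60, three one-eye failures, pilot-line historical misfit. The exponents are 57 + 35.3 − 0.1 = 92.2 (no eye), 3.1 (one eye) and 0 (both). Integrating over p and rho gives P(p<0.05) = .9743.

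**Deciding counts at N=60.** Where two values are shown, SLF is one bilateral case / two one-eye cases, and fit is one bilateral plus one one-eye case / three one-eye cases. For SLF, two of the historical subjects are taken as bilateral.

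| Endpoint, historical placement | Exact P | Exact verdict | Chains passing |
|---|---|---|---|
| SLF, 3 of 5 eyes at a0=0.3 | .9744 / .9739 | fail | 37% / 36% |
| SLF, 2 of 5 at a0=0.3 | .9786 / .9781 | pass | 93% / 91% |
| Fit, misfit at a0=0.1 | .9739 / .9743 | fail | 29% / 41% |
| Fit, misfit at a0=0.3 | .9691 / .9694 | fail | about 2% (three one-eye cases) |

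In rows one and three the gap is 0.0006-0.0011, about half an SE or less.

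**How likely these counts are.** At the planning rates, SLF: .2008 + .0420 = 24%. Fit: .0559 + .0011 = 5.7%. The wrong-verdict chance in the worst SLF placement is .2008×.366 + .0420×.356 = 8.9% (8.1% by a normal approximation). For fit it is .0559×.288 + .0011×.406 = 1.7% (1.9% by the approximation). In the most favourable placements it is essentially zero.

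**Other safety N.** SAP 6.3 counts everyone given a test article, and SAP 8.4 enrols 80 for 60 completers. Taking historical SLF eyes as one-eye cases:

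| Historical SLF eyes at a0=0.3 | Gap nearest .975, N=60 | Smallest gap, even N 60-80 |
|---|---|---|
| 0 | 0.010 | 0.0007 (N=68) |
| 1 | 0.007 | 0.0006 (N=70) |
| 2 | 0.003 | 0.0003 (N=74) |
| 3 | 0.0007 | 0.0007 (N=60) |
| 4 | 0.006 | 0.0002 (N=64) |
| 5 | 0.010 | 0.0007 (N=68) |

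Over every N from 60 to 80 and every placement, the smallest gap is below 0.0021 in 26% of SLF scenarios and 38% of fit scenarios.

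**No-borrowing run.** At N=60 with one one-eye case, exact P is .9751 and 49% of chains pass. This is a sensitivity analysis, not the primary verdict.

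**The plan's own figures.** The plan prints no simulation error to reproduce. Its powers of 80% (SLF) and 90% (fit) are not reproduced under the .975 rule. SLF power is 74.5% with 0-2 historical eyes at a0=0.3 and 50.2% with 3-5; fit power is 85.2%. That mismatch is a separate matter, but the 24-point SLF step is exactly the weight of the two-eye count.

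**The case against.** A reader might infer that simulation error exceeds the gap at the deciding counts for both endpoints whatever the history. The figures do not support this. At N=60 it is so for one of six SLF splits and one of two fit placements.

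A reader might also infer that the seed lets the sponsor choose the result. It does not: the seed is printed in the SAP, the run is reproducible, and the noise favours neither side. The fault is arbitrariness at a near-tie. Evidence at .9744 and at .975 is practically the same, and nothing in the plan is contradictory or uncomputable.

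Thinning is a minor part of the problem. Unthinned chains had an SD of 0.0017-0.0022, so deleting it alone would not resolve gaps of 0.0006-0.0011.

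The strongest objection is that 60 is the completer target, so the safety population will probably be larger. The worst SLF placement then moves away from the line: .9790 at N=64 and .9844/.9849 at N=70. That stands for that placement. It does not clear the plan, because every other SLF split meets a gap of 0.0008 or less at some N in the range. The sponsor knows the split but cannot fix the final safety N.

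**Conclusion.** The point holds conditionally. A Monte Carlo SE of about 0.002 is too coarse for a binary rule at .975 when some boundary counts lie within about half that distance. At those counts the pre-specified seed can set pass or fail for SLF or fit. At N=60 the overall chance of a wrong verdict from noise is about 0-9% for SLF and 0-2% for fit.

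These figures assume the planning rates, the printed priors and weights, and the reading of z given above. The ranges span the historical placements, which the documents do not give. The chain shares come from an approximate random-walk sampler, not from PROC MCMC; the exact probabilities do not depend on any sampler. This is an inexpensive improvement to an all-must-pass decision, not a flaw that invalidates the analysis.

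**What to change.** In SAP 14.2.1, compute P(p<0.05) for both safety endpoints, with and without borrowing, by numerical integration over p and rho, and base the SAP 11.1 decision on that value. With two parameters this takes seconds and has no seed.

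If PROC MCMC is kept, monitor the indicator (p<0.05), drop the thinning, and run until the Monte Carlo SE of that indicator is below a limit stated in the SAP and small relative to the distance from .975. As an illustration only, an SE of 0.0002 needs about .975×.025/0.0002² = 609,000 effective draws; that limit is a choice, not something the documents imply.

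The cost is SAP wording and a short program or a longer run. Subjects, data and procedures are unaffected.
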